A multi-site randomisation design was used, with the FE college as the stratifying variable. Students were randomly allocated on a 1:1:1:1 basis to one of four intervention groups (three treatment and one control). It had been agreed at the outset that students retaking both English and maths would receive texts about one subject only. Therefore those students retaking both were randomly allocated to either one or the other outcome group to ensure an overall balanced design, giving an overall average of 31 students per trial arm per college (15/16 per arm, per subject), i.e. an average of 123 students per FE college.

Focusing the design on one subject per person from those taking dual re-sits protects the analysis from potential spill-over effects. For example, a person receiving an English text treatment reminder might also act upon that reminder to do further work on their maths. If that person's maths exam results were included in the non-texting control group this spill-over reminder effect could bias the impact estimate. By allocating dual resit students either to maths or English and removing their results

⁶ Please see footnote 4 for an explanation of how and why this number deviates from the trial protocol.

on the unallocated subject from the analysis, any spill-over effects on the unallocated subject will not be included in the analysis and so cannot influence the results.

Randomisation to each of the four treatment groups was carried out in Stata MP Version 14, using the `.randomise` command with a maximum of 100 randomisations used to achieve balance on the subject taken. The randomisation was conducted at the end of October 2017 by an independent analyst within the evaluation team. Table 1 provides a breakdown of numbers randomised by college and trial arm.

Table 1: Results of the randomisation

College ⁷	Arm 1	Arm 2	Arm 3	Arm 4	Total English	Total maths	Total per college
College 1	51	51	52	51	104	101	205
College 2	8	8	8	9	22	11	33
College 3	18	18	17	18	49	22	71
College 4	8	9	9	9	15	20	35
College 5	42	43	43	43	84	87	171
College 6	22	22	22	22	45	43	88
College 7	26	26	26	25	67	36	103
College 8	33	33	33	32	44	87	131
College 9	23	23	23	24	80	13	93
College 10	29	28	29	28	53	61	114
College 11	33	32	32	32	51	78	129
College 12	6	6	6	6	14	10	24
College 13	50	49	49	49	77	120	197
College 14	27	28	27	27	19	90	109
College 15	22	22	22	22	58	30	88
College 16	51	51	51	52	147	58	205
College 17	13	13	13	13	19	33	52
College 18	16	16	16	15	27	36	63

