- We assume a total of 31 participating colleges and an average of 60 students per college for each of the three pairwise comparisons, with 30 in each treatment arm and 30 in the control (with a broadly even split between maths and English). This means a total of 930 students in each treatment arm and 930 in the control group; a total of 1860 for each of the three pairwise comparisons.
- Maths and English outcomes (i.e. a pass or fail in the English or maths GCSE resit exam) will be considered together as a single outcome variable.
- We assume equal proportions of students in the treatment and control groups ($P = 0.5$) for each pairwise comparison.
- We anticipate a baseline pass rate of 30% ($\theta = 0.3$)
- We have three separate significance tests for the primary outcome, with each of the three treatment groups separately compared to the control group.
- We assume a nominal Type 1 error rate of 0.05 with a two-tailed test, amended using a Bonferroni adjustment for three separate independent tests, to a value of 0.0167 for each test. The Type II error rate is set at 0.2, giving power of 0.8.
- We assume¹⁴ an intra-cluster correlation coefficient (ρ) of 0.1.
- No between site heterogeneity is expected (i.e. $\omega = 0$).
- No level 1 baseline test covariate has been included in the calculation, for reasons explained below. There are also no level 2 stratification variables because we have treated the colleges as random effects and no preliminary stratification was undertaken for college type.
- We assume no attrition in the design, our rationale for which is explained below.
- The EverFSM MDE calculation combined all three treatment arms and assumed a 20% prevalence per college, giving $(90 \times 0.2) + (30 \times 0.2) = 24$ students per college.

The assumptions for each MDE estimation are given in Table 2, below.

The sample size calculations in Table 2 were originally intended to enable the detection of a seven percentage point increase in the GCSE pass rate, from (an estimated) 30 per cent to 37 per cent.¹⁵ However, the underlying model for the purposes of this power calculation, which we have now changed as described above, assumed, a fixed effects model, with no random variation at Level 2, i.e. colleges represented strata from a population fully defined by the sample.

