Notes: There is no treatment heterogeneity, no covariates entered at either Level 1 or Level 2, the baseline proportion successful is assumed to be 0.3, no attrition – attrition values are assumed to be coded zero. We have assumed a sample size for EverFSM of 0.2 of overall sample size. Treatments A, B and C refer to the situations where A) only the student receives a text, B) only the supporter receives a text, and C) both student and supporter receive the text.

Attrition and Follow-up

Individual level attrition may occur through students formally withdrawing their consent to receive texts or by changing their phone number and not informing the experimental administrators of their new number.¹⁹ Students may also drop-out of college or fail to re-sit their exams. We do not envisage any college level attrition at this point; given that their role in the design is minimal and requires little effort. However, where students withdraw from the experiment either through formally requesting no further texts or by failing to update a changed phone number, we still have their outcome data from the NPD, provided they resit their exam, and we propose to use this in the analysis.²⁰

The design envisages no formal follow-up even though pupils may decide not to take one or both of their resits, or may leave college prior to taking their re-sits. In such cases, we will assign their outcomes to a fail; this is justified because the policy interest is in students passing the exam rather than the reasons for failure (i.e. we make no distinction through not taking and performing poorly in the exam). This procedure helps to avoid potential selection effects that could arise from removing

¹⁷ It was anticipated that BKSB/ ForSkills scores could be used as a measure of baseline academic achievement (as set out on page 7 of the protocol); however, further discussion with colleges suggests that this data will only be available in a very small minority of cases, and thus will not provide a suitable measure. Using KS4 (GCSE) scores was also discussed. However, it was felt that as the new requirement to retake GCSE maths and English specifically targets students who received a grade of D/level 3, baseline GCSE grades were likely to vary very little among the sample, and therefore offer little value. It is not possible to obtain GCSE raw scores (i.e. percentages) via the NPD.

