Where the outcome variable is regressed onto the treatment binary indicator. All analyses will be conducted using the Stata analysis package.

The analysis does not adjust for academic achievement at baseline due to the lack of available data (see footnote 17).

Imbalance at baseline for analysed groups

Randomisation, if conducted correctly, should result in equivalent distributions of characteristics in the treatment and control groups. Any such differences arising will do so by chance. We will explore the potential for chance imbalances first through an inspection of the descriptive statistics of various characteristics, comparing treatment and control groups. Secondly, we will run a statistical model to identify any characteristics associated with any imbalance.

The NPD data received as standard in an NPD extract (i.e. data from Tiers 1 and 2, e.g. age, gender, everFSM) can be used to predict imbalances in the treatment and control group through regressing the treatment/control binary indicator onto the suite of extracted NPD variables. We propose to explore this using the model form (2) above with the logit transform, as described in the text. Any coefficients found to be significant will indicate imbalance and these variables will be included in an extension of model (2) above as a sensitivity test on the impact effect; i.e. we will extend model (2)

with significant predictors from the imbalance model and compare the magnitude of the impact estimate between the two impact estimate models.

Missing data

Based on past experience we anticipate missingness to be relatively low for the outcome variables. Missingness is of concern primarily if the variables with missing data are (i) related to the outcome and (ii) the pattern of missingness differs between treatment and control groups. If variables with missing values are unrelated to outcomes then there is no need to adjust for them. Such an adjustment will not reduce bias but will likely decrease precision through increasing the variance of the impact estimator, either through weighting or imputation variance adjustments.

If variables with missingness relate to outcomes, but the pattern of missingness is the same between treatment and control groups, again there is no need to adjust for missingness. The key concern is whether missingness is related to outcomes and whether the pattern of missingness differs between the treatment and control groups.

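### The primary model leaves out the subject on which allocation was balanced, and the only adjusted model picks its covariates by testing chance imbalance: a small, avoidable loss of precision, not a bias

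*SAP*

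**What the plan says.** - **Allocation.** The Randomisation section makes college the stratifier and says draws were repeated, "with a maximum of 100 randomisations used to achieve balance on the subject taken".
- **Primary model.** Under Primary intention-to-treat (ITT) analysis, model (2) has a treatment indicator and a college effect. The Effect size calculation section confirms that it has no covariates and calls this an advantage, because a relative risk varies with covariate values.
- **Prior attainment.** "The analysis does not adjust for academic achievement at baseline due to the lack of available data (see footnote 17"). Footnote 17 covers three candidate measures. College diagnostic scores exist for very few students, and raw GCSE marks cannot be obtained. Earlier GCSE grades, however, were set aside because "baseline GCSE grades were likely to vary very little among the sample, and therefore offer little value".
- **Adjusted model.** Under Imbalance at baseline for analysed groups, treatment is regressed on the variables in the National Pupil Database (NPD) extract: "Any coefficients found to be significant will indicate imbalance and these variables will be included in an extension of model (2"), as a sensitivity test.
- **Use elsewhere.** The Subgroup analyses section enters subject, gender, EverFSM and number of subjects as main effects, each in its own interaction model.

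**The concern.** An analysis should normally reflect the restrictions placed on its randomisation. If subject predicts passing, balancing it reduces the true variability of the treatment contrast. A model without subject still counts that variation as residual noise, so its standard error is somewhat too large. Other variables likely to predict the result are also left out of the primary models, although the SAP will use them elsewhere.

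The rule for the adjusted model selects on the wrong property. Differences between randomised arms arise by chance, as the SAP itself says, so a significant coefficient shows nothing about whether the variable predicts passing. Subject, balanced by design, would hardly ever qualify. The SAP fixes neither a significance level nor a closed list of variables, so the three comparisons may be adjusted for different things. The impact estimates of the two logit models are then to be compared in size. An odds ratio can shift when a prognostic covariate is added even with perfect balance, so that comparison is hard to read.

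At stake are some precision in the primary test, the usefulness of the one adjusted analysis, and the accuracy of the stated reason for not adjusting.

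**Working it through.** **Inputs (Calculation of sample size, Table 2).** Per-test alpha is 0.0167, two-sided ("We assume a nominal Type 1 error rate of 0.05 with a two-tailed test", then "amended using a Bonferroni adjustment for three separate independent tests, to a value of 0.0167 for each test"). Power: "The Type II error rate is set at 0.2, giving power of 0.8". Control pass rate: "We anticipate a baseline pass rate of 30" per cent, so σ = √(0.3 × 0.7) = 0.458. There are J = 31 colleges, n = 60 students per college in each comparison, P = 0.5, ρ = 0.1, ω = 0, and R² = 0 at both levels.

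**Step 1: reproduce the plan's figure.** With ω = 0, formula (1) gives MDE = M × √[(1 − ρ)(1 − R²) / (P(1 − P)Jn)] × σ. On 30 degrees of freedom, M = 2.535 + 0.854 = 3.389. The root is √(0.9 / (0.25 × 1,860)) = √(0.9 / 465) = 0.0440. So MDE = 3.389 × 0.0440 × 0.458 = 0.0683, or 6.83 points (stated 6.8). The same formula with the EverFSM inputs gives 10.66 (stated 10.7).

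**Step 2: adjust for subject alone.** The SAP gives no pass rate by subject, so the gap d is assumed. With an even split, R² = (d/2)² / 0.21, and the MDE scales by √(1 − R²):

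| Assumed gap | R² | MDE (points) |
|---|---|---|
| 0 | 0 | 6.83 |
| 5 points | 0.003 | 6.82 |
| 10 points | 0.012 | 6.79 |
| 20 points | 0.048 | 6.67 |

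**Step 3: adjust for a fuller set.** The SAP gives no R² either, so this too is assumed:

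| Assumed R² | MDE (points) | Power at 6.83 points | Equivalent extra students |
|---|---|---|---|
| 0 | 6.83 | 0.800 | 0% |
| 0.02 | 6.76 | 0.809 | 2% |
| 0.05 | 6.66 | 0.823 | 5% |
| 0.10 | 6.48 | 0.846 | 11% |

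The last column is 1/(1 − R²) − 1.

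**Step 4: check by simulation.** There were 3,000 trials per setting, with Table 1 college sizes, subject balanced within college, and a linear model with college effects. A further predictor was present in the data but absent from both models shown.

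| Subject gap | Effect | Rejects, without subject | Rejects, with subject |
|---|---|---|---|
| 10 points | none | 1.7% | 1.8% |
| 10 points | 6.8 points | 76.8% | 77.3% |
| 20 points | none | 1.4% | 1.6% |
| 20 points | 6.8 points | 75.1% | 76.9% |

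The simulation error of a null rate is about √(0.0167 × 0.9833 / 3,000) = 0.23 percentage points, so 1.4% against the nominal 1.67% is not decisive alone. It agrees with direct calculation. If the standard error is too large by 1/√(1 − 0.048), the normal critical value of 2.394 acts as 2.394 / 0.976 = 2.453, which gives a two-sided rejection rate of 1.4%.

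**Step 5: the selection rule.** If each variable is tested at 0.05 and the variables are independent (both assumed), the chance of at least one false flag is 1 − 0.95^k. This is 14% for the three variables that the SAP names as examples (age, gender, EverFSM) and 40% for ten.

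**Step 6: the stated reason.** The analysis section attributes the absence of adjustment to unavailability. Footnote 17 supports that for diagnostic scores and raw marks. For earlier GCSE grades it records a judgement about value, resting on the retake requirement being aimed at students with a D or level 3. The eligibility list under Study design requires age 16 or over, enrolment and a planned resit, and sets no prior-grade limit.

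**The case against.** The strongest defence is that a prespecified model containing the stratifier and no other covariates is valid, and that the SAP discloses and explains its choice. The power calculation assumes R² = 0, so it matches the planned model, and its MDE already meets the 7-point target. Covariates chosen by imbalance tests enter only a sensitivity model and cannot move the primary estimate or its p-value. Not everything is in hand: subject and single or dual resit were known at randomisation, but gender and EverFSM await the NPD extract. Restricted range is a reasoned ground for setting earlier grades aside, and the SAP gives no grade distribution that would refute it.

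All of this stands, and it limits the point to efficiency and wording. It does not explain why the balancing variable is absent, why sensitivity covariates should be chosen by imbalance rather than prognosis, or why the analysis section and footnote 17 give different reasons. The objection that a relative risk varies with covariates is met by averaging predicted probabilities. The SAP also concedes that its relative risk already refers to a college at the average level, so leaving covariates out does not make it marginal.

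A reader might infer that the primary result is biased, that the 6.8-point MDE is wrong, or that a large gain is being thrown away. The documents support none of these. Randomisation protects the estimate, the MDE reproduces, and nothing in the SAP gives the R² that a large gain would need. Nor does the uneven subject mix between colleges in Table 1 cause harm by enlarging college variance: with within-college allocation and ω = 0, that variance drops out of formula (1).

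**Conclusion.** The point holds as an avoidable inefficiency with a wording error. The primary test is valid but slightly conservative if subject predicts passing. Subject alone is worth 0.04 points of MDE at a 10-point gap and 0.16 points at a 20-point gap (6.83 to 6.79 or 6.67). A fuller set is worth 0.17 points at R² = 0.05 and 0.35 points at R² = 0.10. These figures rest on assumed gaps and R² values, and on formula (1) as a linear approximation to the logistic model. The degree of conservatism also depends on how closely subject was balanced between arms, which Table 1 does not show.

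Two parts need no assumed value: the selection rule is unsuited to its purpose, and the reason given for not adjusting does not match footnote 17 as regards earlier GCSE grades.

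**What to change.** Settle the following before the outcome extract of autumn 2018:

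1. Prespecify one covariate set for all three primary models: subject and single or dual resit, plus gender and EverFSM from the planned NPD extract. Add the earlier GCSE grade in the resit subject, with a missing category, if it can be obtained in that extract.
2. Obtain the relative risk and risk difference by averaging predicted probabilities under treatment and control.
3. Keep the present unadjusted model as a sensitivity analysis. Describe baseline balance, but drop the significance-based choice of covariates.
4. Correct the stated reason: diagnostic scores and raw marks are unavailable, whereas earlier GCSE grades were set aside because little variation was expected.

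The cost is some SAP wording, a standard post-estimation step in Stata and possibly one further NPD field. The headline model becomes slightly less simple.

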Consequently, to adjust for any missingness in the outcome variables we want first to establish whether variables used to predict missingness are associated with the outcome variable. Once we have identified relevant variables with missingness the second step is to assess whether the pattern of missingness differs between treatment and control groups.

For the first step we will identify the association between our suite of variables in the NPD extract and our outcomes. Secondly, variables that are correlated with outcomes will be entered as predictors²³ into a logistic regression model where the dependent variable is the missing/non-missing indicator on the outcome variable. This will inform us of which predictor variables are related to missingness in the outcomes. The next step will be to enter the treatment indicator and a series of interaction terms between the treatment indicator and those variables with a significant main effect association with missingness. Finally, assuming significant associations are found for some of the interaction terms, we will run a reduced form of the model including only significant interaction terms and their associated main effects from the previous model. From this we will construct a missingness weight as the inverse of the propensity score from the reduced model. We will then rerun models (1) and (2) above to explore the adjustment on the magnitude of the impact estimator. Stata's complex survey suite of models will be used (svyset) in order to adjust appropriately for the weight on the variance estimator of the impact effect.

Non-compliance with intervention

There is no a-priori clear cut measure of the number of texts a student should receive for the treatment to be effective; consequently, we do not have a theoretical basis to assign compliance as a function of the number of texts sent and/or received. However, we can consider the proportion defined as a function of the number of texts received divided by the maximum number of texts issued to an individual. In the first instance we will consider compliance as receiving all texts and non-compliance as anything less than all. Depending upon the distribution of texts received, we will consider lowering the threshold for compliance to less than 100 per cent to a lower threshold and using values above that threshold as compliance and below as non-compliance.²⁴ This will act as a sensitivity test for our compliance estimate.

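### Covariates for the baseline-imbalance sensitivity model are chosen by significance tests of allocation, without regard to prognosis: a modest weakness, confined to that sensitivity analysis

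*SAP*

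**What the plan says.** The primary model, model (2), contains a treatment indicator and a random college effect. It has no covariates: "The analysis does not adjust for academic achievement at baseline due to the lack of available data".

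The SAP section Imbalance at baseline for analysed groups starts from the position that, if randomisation was done properly, "Any such differences arising will do so by chance". It plans a descriptive comparison of the groups, and then a model formed by "regressing the treatment/control binary indicator onto the suite of extracted NPD variables". The candidates are given by example only: "data from Tiers 1 and 2, e.g. age, gender, everFSM". The selection rule is: "Any coefficients found to be significant will indicate imbalance and these variables will be included in an extension of model (2) above". The extended model serves "as a sensitivity test on the impact effect", by comparing the size of its impact estimate with that of the unadjusted model. No significance level is stated for this step.

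The Missing data section works differently. There, association with the outcome is examined first, and only "variables that are correlated with outcomes will be entered as predictors" in the model for missingness. That section also argues that adjusting for something unrelated to the outcome removes no bias and tends to cost precision.

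**The concern.** A chance imbalance moves the treatment contrast by roughly the imbalance multiplied by the covariate's association with passing. The rule looks only at the first factor, and only at whether it crosses a significance threshold. A variable that predicts passing well but falls just short of the threshold is left out. A variable that does not predict passing but falls just beyond it goes in.

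The SAP attributes baseline differences to chance, so when randomisation is valid these tests produce flags at their nominal rate and carry no information about which variables matter. The Missing data section applies the prognostic criterion that is absent here.

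What is at stake is how the sensitivity analysis is read. A report that no coefficient was significant, and so nothing was adjusted, could be taken as evidence that baseline differences do not matter. The rule cannot show that.

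**Working it through.** **Inputs from the SAP (Calculation of sample size).** 31 colleges with 60 students per pairwise comparison, so 930 per arm; pass rate 0.30; intra-cluster correlation 0.1; no treatment heterogeneity and no covariates; power 0.8; 0.0167 per primary test; EverFSM prevalence 20%. For the primary tests the SAP states: "We assume a nominal Type 1 error rate of 0.05 with a two-tailed test", which Bonferroni reduces to 0.05/3 = 0.0167.

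**Assumptions, not in the SAP.** Cut-off for the imbalance test 0.05, with 0.0167 as the alternative; 3 to 10 candidate covariates; pass-rate gaps of 5 to 20 points between covariate levels; 50% prevalence for gender.

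**1. The plan's own figure.** From formula (1), the standard error of a contrast is √[0.9/(0.25 × 1860)] × √(0.3 × 0.7) = 0.0440 × 0.4583 = 2.02 points. Multiplying by the sum of the t quantiles on 30 degrees of freedom, 3.389, gives 6.83 points. The SAP states 6.8, so its figure is reproduced.

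**2. Chance flags.** With valid randomisation and roughly independent coefficients, P(at least one flag) = 1 − (1 − α)^k per comparison.

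| k | α = 0.05 | α = 0.0167 |
|---|---|---|
| 3 | 14% | 5% |
| 5 | 23% | 8% |
| 10 | 40% | 16% |

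Over the three comparisons, which share a control group, simulation gave 33%, 49% and 74% at 0.05 for k = 3, 5 and 10.

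**3. Imbalance left unadjusted.** Write a covariate's standardised chance imbalance as Z ~ N(0,1), flagged when |Z| > c. The share of its variance lying in unflagged imbalances is E[Z²; |Z| < c] = (1 − α) − 2cφ(c).

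- α = 0.05, c = 1.96: 0.950 − 0.229 = 0.721, or 72%.
- α = 0.0167, c = 2.394: 0.983 − 0.109 = 0.875, or 87%.

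**4. Size of what is missed.** The largest unflagged difference in prevalence is c√[2p(1 − p)/930], and the shift in the contrast is about that difference times the pass-rate gap.

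| Covariate | Largest unflagged imbalance at 0.05 | Shift, gap 5 points | Shift, gap 20 points |
|---|---|---|---|
| EverFSM (20%) | 1.96 × 1.855 = 3.6 points | 0.18 | 0.73 |
| Gender (50%) | 1.96 × 2.319 = 4.5 points | 0.23 | 0.91 |

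The maximum of 0.91 points is 0.45 standard errors and 13% of the 6.8-point detectable effect. At a 0.0167 cut-off the shifts run from 0.22 to 1.11 points.

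**5. Same shift, opposite treatment.** A 0.5-point shift from EverFSM needs a 5.0-point imbalance if the gap is 10 points (z = 2.70, flagged at 0.05). It needs only 2.5 points if the gap is 20 points (z = 1.35, not flagged).

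**6. Simulation.** 4,000 trials of 1,860 students; five binary covariates, three prognostic (assumed gaps of 10, 8 and 6 points) and two irrelevant; linear outcome without noise; cut-off 0.05. Flag rates were 5.2% to 5.4% for prognostic and 4.7% to 5.1% for irrelevant covariates. The SD of the chance shift was 0.29 points unadjusted and 0.25 under the rule, so 73% of its variance remained. It was essentially zero with all five covariates always fitted. In the 5% of trials with the largest shifts, 59% of the shift remained on average under the rule.

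**The case against.** The strongest reply is that this is only a sensitivity analysis. That stands: the primary model, its threshold and its decision rule do not depend on this step. A reader might infer that the rule inflates the primary false-positive rate. It does not. Averaged over randomisations, chance imbalance is already allowed for in the nominal 0.0167. Given one particular imbalance the unadjusted test can be off its nominal level, but the screening rule does not cause that, and changing the sensitivity model would not alter it.

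A reader might also build a more alarming example. Take a covariate correlated 0.3 with passing and unbalanced at z = 1.9: the shift is about 1.2 points. But that correlation implies a pass-rate gap of 0.3 × 0.458/0.5 = 27 points for a 50% covariate, or 0.3 × 0.458/0.4 = 34 points for EverFSM. The SAP gives no support for gaps of that size, and expects resit students to be close together academically.

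Nor is this step the plan's only protection against imbalance. Randomisation was stratified by college and could be redrawn up to 100 times to balance subject, and a descriptive comparison is planned. The rule also catches the largest imbalances, so calling it useless would be wrong. If the three comparisons end with different covariates, that does not spoil a planned contrast, because each extended model is compared only with its own unadjusted model.

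Finally, the tested null need not hold exactly in the analysed groups: a student may ask for their data to be withdrawn (footnote 20). With non-sitters counted as fails and kept in the analysis, there is otherwise little room for this. It could justify a check of the allocation process, but not letting that check choose covariates.

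**Conclusion.** The point holds as a modest weakness in a sensitivity analysis. Selection is by significance of allocation, flags under valid randomisation are chance, and prognosis plays no part, although the SAP uses it in its Missing data section. About 72% of the imbalance variance of a prognostic covariate stays unadjusted at a 0.05 cut-off, or 87% at 0.0167.

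That share should not be read as the share of harmful imbalance. It is an average over mostly small imbalances, and whether any one matters depends on prognostic strengths the SAP does not give. Over the assumed gaps of 5 to 20 points, a single unflagged covariate shifts a contrast by at most about 0.2 to 0.9 points, less than half a standard error at the 0.05 cut-off. The cut-off, the number of candidates and the gaps are all assumptions. The change is still worth making, because the replacement is better and nearly free.

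**What to change.** Delete the significance rule. Name one covariate set in advance on prognostic grounds, using variables the SAP already mentions: age, gender, EverFSM, subject, and one versus two subjects. Fit that set in the sensitivity extension of model (2) for all three comparisons, whatever the balance looks like, and report it beside the unadjusted estimate. Keep the descriptive balance table. If a test of the allocation process is wanted, it should not select covariates.

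The cost is a change of wording and slightly more analysis work. The variables are in the planned NPD extract or the randomisation records. The primary analysis stays as it is.
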